3.2.6.2. Imputation Rules for Partial or Missing Start Dates

| Start Date | | Stop Date | | | | | | |
|---------------------|--------------------------------------|---------------------------|---------------------------|--------------------------------------|--------------------------------------|-----------------------------------|-----------------------------------|---------|
| | | Complete: yyyymmdd | | Partial: yyyyymm | | Partial: yyyy | | Missing |
| | | < 1 st dose | ≥ 1 st dose | < 1 st dose yyyyymm | ≥ 1 st dose yyyyymm | < 1 st dose yyyy | ≥ 1 st dose yyyy | |
| Partial: yyyyymm | = 1 st dose yyyyymm | 2 | 1 | 2 | 1 | n/a | 1 | 1 |
| | ≠ 1 st dose yyyyymm | | 2 | | 2 | 2 | 2 | 2 |
| Partial: yyyy | = 1 st dose yyyy | 3 | 1 | 3 | 1 | n/a | 1 | 1 |
| | ≠ 1 st dose yyyy | | 3 | | 3 | 3 | 3 | 3 |
| Missing | | 4 | 1 | 4 | 1 | 4 | 1 | 1 |

- 1 = Impute the date of first dose
- 2 = Impute the first of the month
- 3 = Impute January 1 of the year
- 4 = Impute January 1 of the stop year

3.3. Statistical Analysis

Categorical variables will be summarized in frequency tables, with the counts and percentage of patients in each category. Percentages given in the summary tables will be rounded and thus may not always add up to exactly 100 percent. For continuous variables, summary statistics will include number of patients, mean, standard deviation, first quartile (Q1), median, third quartile (Q3), and minimum and maximum values (range).

EBC Subtype determined by the central assessment will be used for statistical analyses.

3.3.1. Patient Disposition

The patient disposition will be tabulated using the ITT. Frequency count and respective percentages of patients who were in each population (i.e. ITT, Safety, and Evaluable), and discontinued from treatment and/or trial will be summarized by EBC Subtype. The reason for discontinuation (from treatment and/or from trial participation where applicable) will be summarized considering the categories specified in the case report forms. Listings of disposition information and analysis population will be provided as well.

Protocol deviations, including eligibility deviations of the inclusion/exclusion criteria, will be summarized and listed for ITT, by EBC Subtype.

| | | | | | |
|----------------|---------------------------|-----------|----|-----------------|-------------|
| Originated by: | [name] | Revision: | 03 | Effective Date: | 30 Sep 2019 |
| Doc Number: | TRIO030-DM-0025 | | | | |
| Title: | Statistical Analysis Plan | | | | |

3.3.2. Demographics and Disease Characteristics

The following patient demographics and disease characteristics will be summarized and listed for the ITT and Safety Population by EBC Subtype:

Patient Demographics:

- Age, the integer part of [(Date of enrollment – Date of birth) / 365.25]
 - Note: Since only the year of birth is collected (YYYY), we assume the full date to be 31-Dec-YYYY
- Race
- Ethnicity
- Menopausal Status
- Weight at Baseline
- Height at Baseline
- ECOG Status at Baseline

Disease Characteristics:

- Time from Initial Diagnosis to Enrollment
- Primary Tumor Location
- Staging at Initial Diagnosis
- Histopathological Type at Initial Diagnosis
- Histopathological Grade at Initial Diagnosis
- Local Estrogen Receptor Status
- Local Progesterone Receptor Status
- Local HER2 Status

Medical History:

The medical history is coded by the most current version of Medical Dictionary for Regulatory Activities (MedDRA), and will be summarized for ITT by System Organ Class (SOC) and Preferred Term (PT) by EBC Subtype.

3.4. Efficacy Analyses

Not applicable.

3.5. Safety Analyses

Safety analyses will be performed on the **safety population**.

3.5.1. Extent of Exposure

Duration of Treatment, Treatment Exposure, Cumulative Dose and Relative Dose Intensity (RDI) will be summarized by EBC Subtype for the safety population.

- Duration of Treatment (days) = sum of duration of each administration period
 - Duration of each administration period = [(End Date - Start Date) + 1]
- Treatment Exposure (days) = [(Date of last dose - date of first dose) + 1]

| | | | | | |
|----------------|---------------------------|-----------|----|-----------------|-------------|
| Originated by: | [name] | Revision: | 03 | Effective Date: | 30 Sep 2019 |
| Doc Number: | TRIO030-DM-0025 | | | | |
| Title: | Statistical Analysis Plan | | | | |

- Cumulative Dose (mg) = sum of [duration of each administration period × Actual Daily Dose]
- Actual Dose Intensity (mg/day) = (Cumulative Dose) ÷ (Treatment Exposure)
- Planned Dose Intensity (mg/day) = 1200 mg
- RDI (%) = (Actual Dose Intensity ÷ Planned Dose Intensity) × 100

The RDI will be additionally presented categorized (i.e., number and percentage of patients with RDI of < 60%, 60 - < 80%, 80 - < 90%, 90 - < 110%, ≥ 110%).

The number and percentage of patients with dose modifications, along with their respective reasons will be summarized.

The compliance is assessed for the entire treatment period and will be calculated as:

$$\text{Compliance (\%)} = \frac{\text{Number of Tabs Taken}}{\sum[\text{Duration of each administration period} \times (\text{Actual Daily Dose} \div 300)]} \times 100$$

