5.3.2 Standard Treatment Schedule

5.3.2.1 Dosage and Administration

Darolutamide will be given at a dose of 600 mg (2 × 300 mg tablets) b.i.d. to a daily dose of 1,200 mg.

The following timelines will be considered for darolutamide administration (refer to Figure 1: Study Schema):

- Darolutamide shall be administered starting within 5 days of enrollment.
- No more than 42 days should elapse from the day the study-specific tumor sample is taken at initial diagnosis (or in a subsequent procedure) to the day of the first intake of darolutamide (*Note: for patients who already had their initial diagnostic biopsy prior to registration and this procedure has been done according to the protocol requirements, the 42- day window should be counted from the date of such biopsy*).
- Minimum duration of treatment will be 14 days prior to BC surgery or to the pre-NAST biopsy (if NAST is indicated) (*Note: a day of treatment is considered as any day where the patient takes any darolutamide intake*)
- A maximum duration of 21 days of treatment is recommended. It is recommended that the date of BC surgery/pre-NAST biopsy is defined prior to starting protocol treatment. The start date of darolutamide (Day 1) will be derived as minus 14 to 21 days from the scheduled BC surgery/pre-NAST biopsy date.
- Treatment will be given until the day prior to the BC surgery, or the day before pre-NAST biopsy or when npo is ordered, whichever occurs first.
- If for some reason BC surgery/pre-NAST biopsy takes place more than 21 days after treatment start, it is acceptable that patient receives darolutamide for more than 21 days and up to a maximum of 35 days; patient should continue protocol treatment until the day prior to BC surgery/pre-NAST biopsy or npo is ordered. In these cases it is strongly recommended to have BC surgery/pre-NAST biopsy done as soon as possible after 21 days of treatment are completed. Also, in any case that treatment is extended beyond 21 days, TRIO Medical Monitor should be contacted to discuss continuation of treatment and the need for assessments.

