- The first day of darolutamide administration in the study is considered Day 1. On or prior to Day 1 the patient will be provided with a bottle with 140 tablets containing 300 mg of darolutamide each (enough for 35 days of treatment at a daily dose of 1,200 mg). Patient will be instructed that the last protocol treatment intake should be the one in the morning of the Pre-surgery visit. The last darolutamide intake will be on the day prior to BC surgery, or the day before pre-NAST biopsy when the Pre-surgery visit should occur. Exceptions to this rule are when patient is ordered to stop oral intake before the day prior to BC surgery/pre-NAST biopsy, when BC surgery/pre-NAST biopsy is planned for a Monday or the day following a holiday, or in case that performing Pre-surgery visit on the same day of BC surgery/pre-NAST biopsy is required by site due to logistical reasons or patient's/physician's convenience (refer to section 6.4.3 for guidance).

Darolutamide should be taken approximately at the same time each day, twice a day. It is recommended that darolutamide be taken with food; recommendation is to take it with breakfast and dinner each day. Patients will ingest darolutamide whole tablets with water. No tablet should be ingested if it is broken, cracked, or otherwise not intact.

If the patient misses an intake or vomits following darolutamide administration, the missed/vomited dose should be skipped and the patient should take the next intake when scheduled. No “make-up dose” or increased dosing should occur.

If a patient accidentally or intentionally takes a higher daily dose than the one recommended per protocol and up to 1,800 mg (i.e. up to 6 × 300 mg tablets), protocol treatment should continue as scheduled without any dose reduction or skip. For example, if by mistake the patient takes 4 tablets in the first daily intake she can still take 2 tablets in the second daily intake since a total daily dose of 1,800 mg is not exceeded. The Medical Monitor should be contacted for any dose taken that exceeds 1,800 mg daily.

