Appendix 2: Patient Diary Template

See next page. The remainder of this page is intentionally left blank.

Site Staff Instructions

Record the Patient ID.

Minimum duration of treatment with ODM-201 is 14 days, with a recommended maximum duration of 21 days. Treatment must not last more than 35 days.

Record in the below table, the calendar dates (dd/mmm/yyyy, Morning or Evening) corresponding to the initial treatment period with ODM-201 1200 mg per day (Sequence 1).

For grade 1-2 treatment-related AEs only: should any treatment interruption / dose modification take place (to be agreed on with TRIO Medical Monitor), please record in the subsequent row (Sequence 2) the treatment start / stop dates and treatment dose to be taken by the patient. Note: for grade ≥ 3 treatment-related AEs, treatment should be permanently discontinued.

Depending on the day / time when the patient is provided with the ODM-201 bottle, treatment may start with either a Morning or an Evening intake.

The last ODM-201 intake will be on the day prior to breast cancer surgery or before starting neoadjuvant treatment if indicated, in the morning of the Pre-surgery visit (except if the patient is ordered to stop oral intake earlier – please refer to protocol section 6.4.3 “Pre-surgery visit” for guidance).

Please refer to protocol sections 5.3 and 5.4.2 for more details.

Date of ODM-201 bottle dispensation: ____ / ____ / ____

(dd/mmm/yyyy)

Seq.	Treatment Period	Daily Dose	Study Treatment container
1	
From: _____ / _____ / _____ (dd/mmm/yyyy)
 
To: _____ / _____ / _____ (dd/mmm/yyyy)
	
 Morning  Evening
 
 Morning  Evening
 
1200 mg 2 tablets twice a day (with food, at breakfast and dinner)
	
Bottle (containing 140 tablets of ODM-201 300 mg)

2	
From: _____ / _____ / _____ (dd/mmm/yyyy)
 
To: _____ / _____ / _____ (dd/mmm/yyyy)
	
 Morning  Evening
 
 Morning  Evening
 
1200 mg 2 tablets twice a day (with food, at breakfast and dinner)
 
Or
 
 600 mg
 
1 tablet twice a day (with food, at breakfast and dinner)
	

Date of Pre-surgery visit: ____ / ____ / ____

–

(dd/mmm/yyyy)

Date of surgery: ____ / ____ / ____

(dd/mmm/yyyy)

Patient Instructions:

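### SAP 3.5.1 computes cumulative dose, RDI and compliance from whole days, so a fully adherent patient with a one-intake last (and perhaps first) day gets at least one wrong figure

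*SAP*

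**What the plan says.** SAP 3.5.1 (Extent of Exposure) takes whole dates as its unit. The length of a period is given by "Duration of each administration period = [(End Date - Start Date) + 1". Dose follows from it: "Cumulative Dose (mg) = sum of [duration of each administration period × Actual Daily Dose". The RDI time base is "Treatment Exposure (days) = [(Date of last dose - date of first dose) + 1", the plan is "Planned Dose Intensity (mg/day) = 1200 mg", and the ratio is "RDI (%) = (Actual Dose Intensity ÷ Planned Dose Intensity) × 100". Compliance divides tablets taken by the summed product of period length and Actual Daily Dose over 300. Actual Daily Dose is not defined. SAP 3.2.4 leaves duration of treatment out of its general duration rule, so 3.5.1 holds the only definition.

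The protocol works in half-days. Section 5.3.2.1 gives the general rule for stopping: "Patient will be instructed that the last protocol treatment intake should be the one in the morning of the Pre-surgery visit". The diary template (Appendix 2) says that "treatment may start with either a Morning or an Evening intake", and it records Morning or Evening at the start and stop of each dosing sequence. For counting days, section 5.3.2.1 notes that "a day of treatment is considered as any day where the patient takes any darolutamide intake".

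**The concern.** A course under the general rule has one intake (600 mg) on its last day, and also one on its first day if dosing starts in the evening. The SAP credits or plans a full 1,200 mg on those days, so a patient who takes every tablet as instructed does not come out at the correct dose, 100% RDI and 100% compliance together. The two possible meanings of Actual Daily Dose put the error in different places. Unless the term is defined, a reader of the tables cannot tell which column is affected. The relative error is largest for short courses, and this trial sets a minimum of 14 days and a recommended maximum of 21.

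A second issue concerns days. Two periods that share a date would each count it, and a date without any intake inside a period would count as treated.

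**Working it through.** **Inputs.** 300 mg tablets, two per intake, two intakes per full day (protocol 5.3.2.1); start in the morning or evening (Appendix 2); stop in the morning as a general rule (5.3.2.1); formulas from SAP 3.5.1.

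**The plan's own figure.** Protocol 5.3.2.1 says that 140 tablets cover 35 days at 1,200 mg: 35 × 4 = 140. This is reproduced, and it assumes two intakes on every day.

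**Full adherence, no dose change.** Let *n* be the number of calendar days and *h* the number of end days with one intake (0, 1 or 2). Tablets taken are 4*n* − 2*h*; the SAP product corresponds to 4*n*.

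| Days | h | Tablets taken | mg taken | mg at 1,200 for every day | Excess | Tablets taken / 4n |
|---|---|---|---|---|---|---|
| 14 | 0 | 56 | 16,800 | 16,800 | 0% | 100% |
| 14 | 1 | 54 | 16,200 | 16,800 | 3.7% | 96.4% |
| 14 | 2 | 52 | 15,600 | 16,800 | 7.7% | 92.9% |
| 21 | 1 | 82 | 24,600 | 25,200 | 2.4% | 97.6% |
| 21 | 2 | 80 | 24,000 | 25,200 | 5.0% | 95.2% |
| 35 | 1 | 138 | 41,400 | 42,000 | 1.4% | 98.6% |
| 35 | 2 | 136 | 40,800 | 42,000 | 2.9% | 97.1% |

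How the last two columns enter the outputs depends on the undefined term.

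- *Assigned dose.* Cumulative dose is too high by the Excess column, and compliance equals the last column. RDI = (1,200 × *n* ÷ *n*) ÷ 1,200 = 100%. Tablets taken do not enter it, so missed intakes cannot lower it unless they move the first or last dose date or split a period.
- *Dose taken.* Cumulative dose is right, but RDI equals the last column; for *n* = 14 and *h* = 2, 15,600 ÷ 14 ÷ 1,200 = 92.9%. The compliance denominator becomes the tablets taken, so compliance is 100% for everyone.

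**RDI category.** With *h* = 2 the last column is 1 − 1/*n*, which is at least 90% when *n* ≥ 10 (10 days: 36/40 = 90.0%; 9 days: 32/36 = 88.9%). So with full adherence, no dose change and at least 10 days, the category stays at 90 to <110% on either reading.

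**Shared date (illustration; the day of the switch is assumed).** Morning start, morning end, 14 days, assigned dose halved between the morning and evening intakes of day 10, both periods entered with that date.

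- Duration of Treatment: 10 + 5 = 15 days, against a Treatment Exposure of 14.
- Cumulative dose: 10 × 1,200 + 5 × 600 = 15,000 mg. Tablets taken: 36 (days 1–9) + 3 (day 10) + 6 (days 11–13) + 1 (day 14) = 46, or 13,800 mg.
- Compliance: 46/50 = 92.0% despite full adherence.
- RDI: 15,000 ÷ 14 ÷ 1,200 = 89.3%. On scheduled intakes it is 13,800 ÷ (27 × 600) = 85.2%.

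**Date without intake.** If one date in a 14-date period has no intake and the period is not split, the SAP counts 14 days; the protocol's definition gives 13.

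**The case against.** The strongest reply is that the error is small and not universal. Protocol 5.3.2.1 lists exceptions to the morning stop. Under section 6.4.3(b), for surgery on a Monday or after a holiday, intakes continue to the day before the procedure unless oral intake is stopped earlier. The last day can then hold two intakes, and with a morning start the SAP formula is exact. This stands: it would be wrong to infer that every adherent patient is misreported.

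A reader might also infer that the formula moves nearly adherent patients across the 90% RDI boundary. Take an evening starter on 14 days who misses one intake: 50/56 = 89.3%, against 50/52 = 96.2% of scheduled tablets. That 89.3% is an RDI only on the dose-taken reading. On the assigned-dose reading, arguably the more natural one because compliance sets tablets taken against it, RDI prints 100% and 89.3% is compliance, which has no categories.

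A further inference is that patients with 13 treatment days would be admitted as evaluable. The documents do not show this. SAP 3.1.3 does not refer to the 3.5.1 variable, protocol 5.3.2.1 already defines a treatment day, and the Steering Committee assesses evaluability (protocol 8.5).

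Double counting of dates is not established either: the Morning/Evening fields are in the diary template, and the eCRF entry rules are not in the documents.

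Finally, protocol 8.4 bases safety mainly on adverse event frequency, and SAP 2.3 states that subgroups are not compared. These points limit the consequences, but they do not make the formulas right under the general rule.

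**Conclusion.** The point holds for patients who follow the general rule of a morning last intake. For such a patient with full adherence, at least one of cumulative dose, RDI and compliance is wrong on either reading of Actual Daily Dose. The discrepancy is one intake (600 mg) with a morning start and two (1,200 mg) with an evening start. The usual one-intake case overstates dose by 3.7% at 14 days and 2.4% at 21; the 7.7% figure needs both an evening start and a 14-day course.

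The calendar-day problems are conditional. They arise if periods are entered with a shared date, or if a fully missed day does not split a period. They bear on evaluability only if the 3.5.1 variable is used for the 14-day criterion. The affected outputs are descriptive, so this is a correction worth making rather than a threat to the trial's conclusions.

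**What to change.** In SAP 3.5.1, count intakes for dose and dates for duration:

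- Cumulative Dose = 300 mg × tablets taken. The compliance formula already needs this count.
- Compliance denominator = tablets scheduled at the assigned dose, with a one-intake first or last day counted as one intake.
- RDI = Cumulative Dose ÷ (600 mg × scheduled intakes from first to last dose). State that this count includes intake times during a hold or at a reduced dose, so that RDI still falls with either.
- Duration of Treatment = number of distinct dates with any intake, as protocol 5.3.2.1 defines a treatment day. Use the same count for the 14-day criterion in SAP 3.1.3.

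Check: a fully adherent 14-day patient with an evening start and morning stop gets 15,600 mg, RDI 15,600 ÷ (600 × 26) = 100% and compliance 52/52 = 100%. In the shared-date illustration, duration becomes 14 days and compliance 46/46 = 100%.

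The cost is SAP wording and programming if Morning/Evening and tablet counts are in the database. The documents do not show that they are, and enrolment had closed (14 February 2019) before this SAP revision took effect (30 September 2019). If the fields were not captured, they must be taken from the diaries. No dosing rule changes.

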3.5.2. Adverse Events (AEs)

AE information will be collected from the time the patient signs the informed consent and continues throughout the trial until EoS. After EoS, AE/SAE information will be collected only if related to the study treatment.

The reported AE term will be coded using the current version of the MedDRA. The severity of AE will be presented as reported by the Investigator based on National Cancer Institute (NCI) Common Terminology Criteria for Adverse Events (CTCAE) grades version 4.03.

Treatment-Emergent Adverse Events (TEAEs) is defined as AEs that start on or after the first dose of investigational treatment or AEs that start before the first dose of treatment but worsened after investigational treatment is initiated.

Incidence of TEAE will be tabulated by SOC, PT for:

- All TEAEs
- TEAEs by relationship to investigational treatment and maximum severity grade
- TEAEs with action taken dose reduced/drug interrupted
- TEAEs with action taken drug withdrawn
- Serious Adverse Events (SAE) (not Serious TEAEs)
- AEs leading to deaths (not Fatal TEAEs) – An AE is considered as leading to death if it reported as Grade 5.

In the event a patient experiences repeat episodes of the same AE according to PT, the event with the highest severity grade will be used for purposes of incidence tabulations.

Detailed listings for all AEs will be provided, including listing with AEs per cohort. A flag will be used to identify which AE is considered as treatment emergent.

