6.4.5 End of Study Visit

EoS visit must be scheduled 30 days (+/- 3 days) after the last intake of darolutamide, even for patients who did not complete the minimum 14 days of protocol treatment.

The primary purpose of this visit is to follow-up any AEs/laboratory abnormality ongoing at the time of protocol treatment discontinuation and to assess any new AEs/abnormality that may have occurred since protocol treatment discontinuation. Symptom-directed physical examination, ECOG PS assessment and hematology/blood chemistry should be done at this visit. All AEs will be collected (even if due to neoadjuvant treatment, surgery or adjuvant treatment, regardless of the relationship to darolutamide), as well as relevant concomitant treatment according to rules in section 6.5.4.

EoS will be the last study visit with the exception of patients with protocol treatment-related AEs/SAEs that are ongoing at the time of the EoS visit. In these cases, monitoring of these events will continue as clinically indicated until (a) the events have resolved or (b) the events have reached a status which, in the Investigator's opinion, is unlikely to resolve due to the nature of the condition and/or the patient's underlying disease. Frequency of visits will be according to Investigator's judgment.

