4.1. Planned Tables

| Title | Population | Description |
|---------------------|------------|---|
| Patient Disposition | ITT | Tabulates the disposition of all patients by EBC Subtype, including the number of patients in each population set as well as the number of patients discontinued from investigational treatment, and the number of patients discontinued from trial. The reason for drug discontinuation and trial discontinuation will also be summarized. |
| Protocol Deviations | ITT | Tabulate the number of patients who reported protocol deviations by deviation category for each |

| Title | Population | Description |
|---------------------------------|---------------|---|
| | | EBC Subtype. |
| Eligibility Deviations | ITT | Tabulates the number of patients who violates inclusion/exclusion criteria by criterion for each EBC Subtype. |
| Patient Demographics | ITT Safety | Tabulates summary statistics of the demographics (age, race, ethnicity, menopausal status, weight, height and ECOG status at baseline). |
| Disease Characteristics | ITT | Tabulates summary statistics for time from initial diagnosis to enrollment, primary tumor location, staging at initial diagnosis, histopathological type at initial diagnosis, histopathological grade at initial diagnosis, hormonal receptor status, and HER2 status. |
| Medical History | ITT | Summarizes medical history by SOC and PT for each EBC Subtype. |
| Study Drug Exposure | Safety | Summarizes the duration of treatment, cumulative dose, and RDI by EBC Subtype. The number of dose modifications will also be summarized. |
| Compliance | Safety | Compliance assessment will be summarized. |
| TEAEs Overview | Safety | Tabulates the number of patients with TEAEs, Related TEAEs, Grade 3 / 4 TEAEs, TEAEs with action taken as dose reduced or drug interrupted, AEs leading to drug withdrawn, SAE, Fatal AE. |
| TEAEs | Safety | Summary of number of patients and events by SOC and PT for each EBC Subtype. |
| TEAEs per Maximum Grade | Safety | Summary by SOC and PT of number of patients and events for each EBC Subtype. |
| Related TEAEs | Safety | Summary by SOC and PT of number of patients and events for each EBC Subtype. |
| Related TEAEs per Maximum Grade | Safety | Summary by SOC and PT of number of patients and events for each EBC Subtype. |
| Grade 3 / 4 TEAEs | Safety | Summary by SOC and PT of number of patients and events for each EBC Subtype. |

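### The treatment-emergent window runs on to the End of Study visit, so the all-cause AE tables mix on-drug events with those of surgery, NAST and adjuvant therapy

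*SAP*

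**What the plan says.** SAP 3.5.2 fixes where treatment emergence begins: "Treatment-Emergent Adverse Events (TEAEs) is defined as AEs that start on or after the first dose of investigational treatment". Events that began earlier but worsened after that dose are added. No last day is given. The same section bounds collection: "AE information will be collected from the time the patient signs the informed consent and continues throughout the trial until EoS", and then "After EoS, AE/SAE information will be collected only if related to the study treatment".

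Protocol 6.4.5 places the closing visit: "EoS visit must be scheduled 30 days (+/- 3 days) after the last intake of darolutamide". It also settles what is gathered up to then: "All AEs will be collected (even if due to neoadjuvant treatment, surgery or adjuvant treatment, regardless of the relationship to darolutamide". Table 3 in Protocol 7.1.1 agrees: from first intake to EoS, every event is reported whatever its relationship to the drug.

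On timing, Protocol 5.3.2.1 says "Treatment will be given until the day prior to the BC surgery, or the day before pre-NAST biopsy", or earlier if oral intake is stopped. It also says "Minimum duration of treatment will be 14 days prior to BC surgery or to the pre-NAST biopsy". The recommended maximum is 21 days and the absolute maximum 35. The German synopsis in SAP Appendix 5.2 expects 14 days. Protocol 5.3.4 says that surgery, NAST and post-surgical therapy are not protocol treatment.

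SAP 4.1 describes the TEAE table as "Summary of number of patients and events by SOC and PT for each EBC Subtype". The maximum-grade, Related and Grade 3/4 tables have the same layout. None is split by period. For repeat episodes of one preferred term, SAP 3.5.2 counts the highest grade.

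**The concern.** The SAP exists to analyse the only secondary objective, the safety and tolerability of short-term darolutamide. Under its rules a complication of surgery or a toxicity of NAST is labelled treatment-emergent just as an event on day 5 of darolutamide is. No planned AE table isolates by time what happened while patients were taking the drug.

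The flag also removes very little. Before first intake, Table 3 asks for non-serious events only if they are related to study participation, so the all-TEAE table is close to a table of every reported AE. The highest-grade rule adds to the mixing. A patient with Grade 1 fatigue on darolutamide and Grade 3 fatigue on NAST appears once, at Grade 3. Fatigue is the most common AE that Protocol 1.2 reports for this drug.

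**Working it through.** The documents give no figure for this point, so there is none to reproduce. The check has four steps.

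**1. Following an event through the rules.** Take a hypothetical Grade 3 wound infection a week after surgery.
- Onset is after first dose, so it is a TEAE (SAP 3.5.2).
- It must be collected (Protocol 6.4.5 and Table 3).
- Protocol 7.1.2 excludes planned surgery and the condition leading to it, but not complications.
- It enters the TEAE, maximum-grade and Grade 3/4 tables. It stays out of the Related tables only if the investigator records no relationship.

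**2. Share of the window that is off drug.** Let T be treatment days and F the days from last intake to EoS (30, range 27 to 33). Share = F/(T + F).

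| T (days) | F = 30 | F = 27 to 33 |
|---|---|---|
| 14 | 30/44 = 68.2% | 65.9% to 70.2% |
| 21 | 30/51 = 58.8% | 56.2% to 61.1% |
| 35 | 30/65 = 46.2% | 43.5% to 48.5% |

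**3. Could drug persistence justify the whole window?** Protocol 1.2 gives a mean half-life of 11.5 to 16.1 hours. Taking five half-lives as washout (a convention, not a rule in the documents):
- 5 × 11.5/24 = 2.40 days, leaving (30 − 2.40)/30 = 92.0% of follow-up beyond washout;
- 5 × 16.1/24 = 3.35 days, leaving (30 − 3.35)/30 = 88.8%.

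Persistence covers only the first few days. Late effects remain possible, but they do not make the whole period on-drug time.

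**4. What this could do to the any-TEAE row.** Let a be the probability of any AE on drug and b the probability of any AE afterwards. Both are assumed, and taken as independent. The row reads 1 − (1 − a)(1 − b). The fraction of those patients who are there only because of a later event is (1 − a)b divided by that.

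| a | b | Any TEAE | Later event only, as share of patients with a TEAE |
|---|---|---|---|
| 10% | 20% | 28% | 64% |
| 10% | 50% | 55% | 82% |
| 10% | 80% | 82% | 88% |
| 30% | 20% | 44% | 32% |
| 30% | 50% | 65% | 54% |
| 30% | 80% | 86% | 65% |
| 50% | 20% | 60% | 17% |
| 50% | 50% | 75% | 33% |
| 50% | 80% | 90% | 44% |

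With all 36 enrolled patients as denominator, a = 30% and b = 50% gives 0.65 × 36 = 23.4 patients in the row, against 0.30 × 36 = 10.8 with onset on drug. Across the grid the later-only share runs from 17% to 88%, so the assumed rates decide whether such patients are a majority.

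**The case against.** Much of the opposing case stands.

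- **The window does close.** Collection stops at EoS, apart from related events. It would be wrong to read the definition as running without limit, and the shares above depend on that closure.
- **All-cause reporting is what the protocol asks for.** Protocol 6.4.5 wants new events of any cause, and Protocol 8.4 plans AE incidence by class, term and grade. Peri-operative events after exposure also matter in a presurgical study. This supports keeping the overall tables; it does not argue against a split beside them.
- **Other outputs help.** Related TEAEs are tabulated, also by maximum grade. The action-taken tables depend on a change to darolutamide, so events after the last dose should not populate them. Listings carry start dates, and 36 patients can be checked by hand. However, the Related tables rest on a yes/no judgement in an open-label study without a control arm (Protocol 7.2.2), and a listing leaves the reader to rebuild the table.
- **Days are not events.** A reader might infer that the tables would mainly describe surgery and chemotherapy. The documents do not show this. At a = 50%, no row of the grid gives a later-only majority. The one any-AE rate in the documents, 93.9% in Protocol 1.2, comes from earlier trials chiefly in men with prostate cancer. It is not transferable, but it lends no support to a low on-drug rate.
- **Subtype contrasts.** A reader might also infer that a different mix of surgery and NAST between subtypes would pass for a subtype difference in toxicity. SAP 2.3 says the safety profile involves no comparison between subgroups, and neither document gives that mix. The columns are descriptive, so this remains conjecture.

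**Conclusion.** The point holds in a limited form. Treatment emergence has no end other than EoS, and as specified the all-TEAE, maximum-grade and Grade 3/4 tables cannot separate short-term darolutamide exposure from the surgery and therapy that follow it. Off-drug time is 59% to 68% of the window at 21 to 14 treatment days, and 46% at 35 days. This rests on protocol timing alone: EoS at 30 days, with surgery or biopsy the day after the last intake. How far the incidence figures would move cannot be determined from the documents; the grid is an illustration on assumed rates.

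It is a recommended improvement, not a must-fix. The analysis is descriptive and single-arm, with no test or threshold. Related events are tabulated separately, and dated records allow the tables to be recut. It is more than a missing detail, because following the stated rule exactly still leaves the secondary objective without a table confined to the exposure period.

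**What to change.** In SAP 3.5.2 and 4.1, add a period flag and present the all-TEAE, maximum-grade, Grade 3/4 and SAE tables by:

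- (i) onset from first intake to before the earliest of BC surgery, pre-NAST biopsy or start of non-protocol anticancer therapy;
- (ii) onset from that point to EoS.

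Take maximum grade within each period. Read the secondary objective from (i) together with the Related tables. Keep the overall tables as planned, and leave the action-taken tables unsplit.

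The SAP should also state:

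- **Same-day events.** Protocol 7.2.1 lists start and stop dates, not times, so events on the day of surgery or biopsy need a rule.
- **Imputed start dates.** SAP 3.2.6.2 moves many partial dates to the first dose or to the first of the month. Either can pull a post-surgical event into (i), so such events should be assigned by a stated rule and marked.
- **Events outside both periods.** The SAE table is not limited to TEAEs, so SAEs before first intake need a place, as do related events reported after EoS.
- **Dates on the eCRF.** The surgery date is on the diary form (Appendix 2). Anticancer therapy before surgery or biopsy falls under Protocol 5.5.2 and is recorded through 6.5.4. The eCRF is not shown, so the sponsor should confirm these fields and the biopsy date.

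The cost is one derived variable, some SAP wording and a few more tables, with no new data if the dates are confirmed. Late drug effects would fall in (ii), where they are still shown. Because Protocol 7.2.1 records the worst grade per event, a single record that begins in (i) and worsens later carries its worst grade into (i); a footnote should say so.
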